3.4.3 Late Life Function and Disability Instrument: Function Component (LLFDI-FC)

The Function Component of the Late-Life Function and Disability Instrument (LLFDI-FC) is a widely used patient-reported outcome of physical function.^{14 15} It comprehensively assesses discrete functional tasks and operationalizes disability in important life roles beyond the narrow construct of activities of daily living. Extensive evidence supports its construct validity and sensitivity to change among various clinical populations of community-dwelling older adults.¹⁶ The instrument will be administered over the phone by the research personnel at each follow-up, preoperatively and postoperatively. Three additional questions will be also asked to explore life space mobility (being just outside the house, being in the neighborhood, and being outside

the neighborhood), which will also capture changes in social distancing policy that we expect will happen over the study period. At the end of the mobility questionnaire, the participants will be also asked whether there have been changes in their ability of performing basic and instrumental activities of daily living.

3.4.4 Geriatric Depression Scale (GDS)

The short form (15-item) version of the GDS¹⁷ is widely used instrument, which has demonstrated good reliability and validity in assessing depressive symptoms in older adults. The GDS Short Form takes an average of 5 to 7 min to complete and will be administered by the research personnel on the phone.

3.4.5 Numeric Pain Rating Scale (NPRS)

The Numerical Pain Rating Scale (NPRS) is a rapid subjective measure of pain in which individuals rate their pain on an eleven-point numerical scale. The scale is composed of 0 (no pain at all) to 10 (worst imaginable pain). Correlation with other pain-assessment tools and feasibility of its use also in telephone interviews, have been demonstrated.¹⁸ The NPRS will be administered by the research personnel on the phone.

3.5 Sample size

The slowdown of the operating rooms due to COVID-19 started in mid-March, and it will last at least until the end of June or July at the participating sites. We expect to recruit 330 participants between May and August 2020. This sample size will be sufficient to test our primary hypothesis that, on average, in our population, the cognitive performance at 6 months after surgery will be worse, in a clinically significant way, compared to what we would expect based on the preoperative trajectory. We will base our primary hypothesis on the performance at the *One-Back Task (OBK)* of the CBB, at 6 months after surgery. The *OBK* assesses working memory, which is a cognitive domain often found altered in the context of postoperative cognitive dysfunction. It uses a well-validated n-back paradigm with stimuli from playing cards. The subject is asked whether the card displayed in the center of the screen is the same as the card presented immediately before. The subject responds by pressing the “yes” or “no” key. The primary outcome variable for this test is accuracy of correct response, normalized using an arcsine square-root transformation. In **APPENDIX II** we provide a table summarizing the clinical relevance of the test and its results, with data on the difference in performance between healthy older adults, and older adults with mild cognitive impairment (MCI) or dementia based on standardized neuropsychological assessment.^{13 19} Based on the literature, a typical score of healthy older adults is 1.35; the average difference, at one time point, in the *OBK* score, between healthy older adults and older adults with mild cognitive impairment (MCI), and older adults with dementia, is, respectively, 0.07 and 0.17.^{13 19} We hypothesize that in our study population we will see a preoperative trajectory, which, if it continued, unchanged, after surgery (H_0), would lead to an average decrease in OBK score of 0.009 over 6 months. This is still consistent with a decline over time compared with what we would expect on average in a healthy older population.^{13 19} Our hypothesis (H_1) is that surgery will change the preoperative trajectory so that at 6 months after surgery we will instead see an average decrease, compared with right before surgery, of 0.035 (which would correspond to the average change in a hypothetical population in which 40% of subjects experience a decline of at least 0.07, 50% no

change, and 10% an improvement of 0.07). Based on a test of comparison of means in one sample, with an alpha error of 0.05 (2-tailed), and a standard deviation for the OBK score of 0.16,¹³ to enrol 330 subjects will be sufficient to test our hypothesis with 80% of power, even in case of an attrition rate as high as 10%.

Recruiting 330 participants is a feasible goal based on the current status of knowledge about the COVID-19 contingency plan. The lockdown of the operating rooms started in March and will last at least until the end of June, or longer, depending on the participating site. During the lockdown, we expect to be able to enroll at least 120 participants at McMaster sites, and 30-50 participants at each of the other participating sites. Even when the operating rooms will reopen to more elective surgeries in the next months, this will happen slowly, so that we expect a carryover of the lockdown at least until the end of the summer. Moreover, it is projected that, if countries increase their normal surgical volume by 20% post-pandemic, it would take a median 45 weeks to clear the backlog of operations resulting from COVID-19 disruption.²⁰ Therefore should we see a recruitment rate slower than expected, for any reason, we will extend our recruitment period to beyond the summer.

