impact of surgery can last as long as one year,² we will repeat the analysis including also the change between 6 and 12 months after surgery. In our regression models, we will use estimates of error variance obtained from bootstrap techniques using 1000 bootstrap samples. We will analyze the performance at each task separately, and then combining the 4 scores into one unique measure of performance. We will explore whether clinically significant changes have occurred at any time point. There is no standard definition for what is a clinically significant perioperative decline across different tests.^{24 25} In addition to the change as defined in our sample size calculation (i.e. a change in score equal to or greater than the average difference in scores between a healthy older adult and a subject with MCI), we will consider also 2 most commonly adopted definitions, i.e. 1) a change of $\geq 20\%$ in test scores,²⁶ and 2) a reliable change index (RCI) of ≥ 1.65 . The RCI is an index commonly used in neuropsychology,²⁷ and also in studies using the CBB,¹³ calculated by dividing the individual's test-retest difference score by the standard error of that difference score, and can be interpreted as a standard Z score. The cut-off of RCI=1.65 is the point beyond which 5% of the values from the normal sample population will fall (i.e. $P<0.05$, one tailed test). We will compare the performance scores at each time point with the preceding time points, and evaluate the changes based upon these criteria. We will provide the number and percentage of patients experiencing a cognitive decline based on these definitions at each of the segments of the observation period. We will also compare our study population data with existing age-stratified normative data for the CBB.²⁸

In our primary analyses, we will include only patients who completed ≥ 2 assessments preoperatively and ≥ 3 assessments (i.e. 1, 3, and 6 months) postoperatively. Secondarily, we will repeat our analysis dealing with missing data 1) through multiple imputation techniques; and 2) using a method of evidence-informed data imputation, previously implemented in our studies, which takes onto account the reason for the missing data.³

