APPENDIX I. Study timeline, measurements, and data collection

Measurement	Before surgery				After surgery							
	- ≥6 weeks	Monthly		+1 mo		+3 mo		+6 mo		+12 mo		
	Videocoference with research team	Reminder call with research team*	Patient self-administered	Reminder call with research team*	Patient self-administered	Reminder call with research team*	Patient self-administered	Reminder call with research team*	Patient self-administered	Reminder call with research team*	Patient self-administered	
Verbal consent (confirmation)	x	x		x		x		x		x		
Sociodemographic and clinical data	x											
Intercurrent clinical events**		x		x		x		x		x		
Information on index surgery				x								
Cogstate Brief Battery (CBB)			x		x		x		x		x	
Change in activities and participation due to COVID-19	x											
Late-Life Function and Disability Instrument (LLFDI-FC) and life space mobility		x		x		x		x		x		
Geriatric Depression Scale (GDS)		x		x		x		x		x		
Numeric Pain Rating Scale (NPRS)		x		x		x		x		x		

*0-3 days before the expected self-administered cognitive assessment

**hospital admissions, ED visits, visits to urgent care, changes in medications

APPENDIX II. Performance at the Cogstate One-Back Task (OBK): interpretation and clinical relevance of changes in score

From Lim 2013¹³ and Mackin 2018¹⁹

Baseline score (SD) in HA	Average difference in score between HA and persons with MCI at any time point (Cohen's d)	Average difference in score between HA and persons with dementia at any time point (Cohen's d)	Score change per every additional year of age (population level)
1.35 (0.16)	0.07 (0.60)	0.17 (2.40)	-0.004

HA – healthy older adults

MCI - subjects with mild cognitive impairment

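### Section 3.5: the 40/50/10 population given as the basis for the 0.035 decline averages 0.021 at the printed 0.07, and reaches 0.035 only with an unstated decliner mean of 0.105

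*Combined protocol and SAP*

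**What the plan says.** Section 3.5 rests the primary hypothesis on the One-Back accuracy score 6 months after surgery. Under H0 the preoperative trajectory continues and "would lead to an average decrease in OBK score of 0.009 over 6 months". Under H1 the mean decrease is 0.035. A parenthesis gives the only basis for that value: it is said to correspond to "the average change in a hypothetical population in which 40% of subjects experience a decline of at least 0.07", half show no change, "and 10% an improvement of 0.07".

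The calculation that follows is a one-sample comparison of means at a two-sided alpha of 0.05, using "a standard deviation for the OBK score of 0.16". The section concludes that 330 enrolled patients give 80% power with up to 10% attrition.

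The 0.07 is the mean difference between healthy older adults and those with mild cognitive impairment (MCI), given in section 3.5 and Appendix II. Section 3.6.1 refers back to the sample size definition and uses this difference as a cut-off: "a change in score equal to or greater than the average difference in scores between a healthy older adult and a subject with MCI".

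**The concern.** A reader who multiplies out the printed percentages and the printed 0.07 gets 0.021, not 0.035. The parenthesis sets only a minimum loss for the 40% who decline, and a minimum does not fix a mean. The scenario is therefore compatible with any average decline from 0.021 upward and cannot support 0.035 in particular.

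What is at stake is the power statement. The objectives in section 2 are to describe and explore, but section 3.5 also states a primary hypothesis and says that 330 patients are enough to test it. If the 6-month comparison shows no clear difference, readers will turn to the 80% figure, and they need to know that it assumes decliners lose half as much again as the threshold.

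**Working it through.** **Inputs (section 3.5).** H0 mean decrease 0.009; H1 mean decrease 0.035; SD 0.16; two-sided alpha 0.05; power 80%; attrition 10%; 330 enrolled. Scenario: 40% lose at least 0.07, 50% do not change, 10% gain 0.07.

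**1. Reproduce the plan's sample size.**
- Net difference: 0.035 - 0.009 = 0.026.
- n = (1.960 + 0.842)^2 x 0.16^2 / 0.026^2 = 297.2 analysed.
- Enrolled: 297.2 / 0.90 = 330. (Rounding up at each step gives 298 and then 332; the difference is rounding only.)
- Check: 330 x 0.90 = 297. Power = Phi(0.026 x sqrt(297) / 0.16 - 1.960) = Phi(0.84) = 0.80. The one-sample t-test gives 0.797.

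So 330 follows from 0.035.

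**2. Average of the scenario.** Let m be the mean loss among decliners, and take no change as 0.
- Mean decline = 0.40 x m + 0.50 x 0 - 0.10 x 0.07.
- At m = 0.07: 0.028 - 0.007 = **0.021**. This is the minimum the wording allows.
- Net of H0: 0.021 - 0.009 = 0.012, which is 46% of 0.026.

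**3. What 0.035 requires.**
- m = (0.035 + 0.007) / 0.40 = **0.105**.
- 0.105 / 0.07 = 1.5 times the healthy-to-MCI difference. The value 0.105 appears nowhere in the documents.
- For comparison, 0.40 x 0.07 + 0.10 x 0.07 = 0.028 + 0.007 = 0.035 exactly. This is the result if the improvers are added instead of subtracted.

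**4. Power at the floor.** With 297 analysed and SD 0.16:
- Power = Phi(0.012 x sqrt(297) / 0.16 - 1.960) = Phi(1.293 - 1.960) = Phi(-0.667) = **0.25** (one-sample t-test: 0.251).
- This treats the three classes as true mean changes, with enough variation around them to bring the total SD of change to 0.16. The three point values alone have SD sqrt(0.5 x 0.07^2 - 0.021^2) = 0.045.

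**The case against.** The strongest reply is that nothing is miscalculated. The text sets a minimum loss for decliners, calls the population hypothetical, and 330 is right for 0.035. This stands in part: 0.021 is a floor, and 0.035 is not strictly contradicted. It does not supply 0.035, because the step from a minimum of 0.07 to a mean of 0.105 is missing.

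A second reply is that 0.105 depends on reading no change as exactly zero. If the unchanged half drifted down by k on average, decliners would need (0.042 - 0.5k)/0.40. That is 0.094 at k = 0.009 (the plan's own H0 decrease) and 0.070 at k = 0.028. This is correct, so 0.105 must be given with its condition. But the plan states no such drift either.

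A third reply concerns the 25%. The floor scenario taken literally has SD 0.045, and with that SD, 297 patients would give power above 99% for 0.012. Moreover, if observed changes were normal with mean 0.035 and SD 0.16 (an assumption), about 41% would fall by 0.07 or more, and those patients would average about 0.19. So 0.105 need not be a demanding value for observed change, although that model does not reproduce the 10% who improve. This stands as a limit on the 25%: it holds only for classes of true mean change with other variation on top. It does not make the printed parenthesis yield 0.035.

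**Conclusion.** The stated basis for the effect size does not lead to the effect size used. At the printed 0.07 the scenario averages 0.021. It reaches 0.035 only if decliners average 0.105, taking no change as 0 and the improvement as exactly 0.07, and the documents give no reason for that mean. The 80% power is for a net difference of 0.026. At the floor (net 0.012) it is about 25%, given SD 0.16, 297 analysed, and the reading of the classes set out in the working.

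Three stronger conclusions might be inferred, and the documents do not support them:
- **That the sample size is wrong or the study must be larger.** At net 0.012 the formula gives (1.960 + 0.842)^2 x 0.16^2 / 0.012^2, or about 1,396 analysed. But 0.012 is the minimum compatible with the wording, not the plan's target, and 330 is correct for the target as stated.
- **That the study has 25% power.** That figure belongs to the extreme case in which every decliner's true loss is exactly 0.07.
- **That a sign slip produced 0.035.** Adding the improvers gives exactly 0.035, but the documents do not show how the value was obtained.

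Whether 0.16 is a suitable SD for a 6-month change is a separate question, and this point does not rest on it. The point should be fixed, but its reach is limited to the justification in section 3.5.

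**What to change.** In section 3.5, replace the parenthesis and add one sentence, for example:

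> With no change taken as 0, a population in which 40% decline, 50% are unchanged and 10% improve by 0.07 averages a decline of 0.021 if each decliner loses 0.07, and 0.035 only if decliners average 0.105 [reason]. The 80% power is for a net difference of 0.026; with SD 0.16 and 297 analysed it is about 25% for a net difference of 0.012, taking the three classes as true mean changes and 0.16 as the total SD of change.

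If 0.105 is kept, the sponsor should justify it. If it cannot be justified, the section should say that the scenario does not support 0.035 and give whatever other basis there is. Choosing a new split only because it reproduces 0.035 (60/30/10 at 0.07, for instance, gives 0.042 - 0.007 = 0.035) would be no better support. More patients should not be enrolled on this ground.

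The cost is a reworded parenthesis and one sentence. The downside is a power statement that looks less favourable. Enrolment, data collection and the planned analyses do not change.

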While for some surgeries, a waiting time to surgery of months is not an unusual eventuality (e.g., some elective orthopaedic surgeries), this is a more unique circumstance for other major elective noncardiac surgeries. Therefore, to identify surgical candidates time before their surgery, and follow them up for a certain time before their surgery is often impracticable. Due to the COVID-19 contingency, we now have a sample of patients that, due to the deferral of their surgery we are capable of following and assessing for their cognitive status before they receive their surgery, for one to a few months. In this way, we will be able to draw preoperative individual-specific trajectories of cognitive performance, which represent an intra-individual comparison to the postoperative cognitive performance, to evaluate the relative and absolute impact of surgery on our older patients.

We expect that the COVID-19 pandemic, and the imposed social distancing, is having an impact on older patient lives, and also on older patients that are waiting for their surgery. Changes in their ability to live a normal life because of the current restrictions might translate into changes in their physical performance, and might have an impact on their mood and also on their perception of pain, and eventually translate into changes in their cognitive performance. The deferral of their surgery *per se*, and the possible adoption of adjuvant

therapies in the meantime, might have, at least theoretically, an influence on their overall performance. For all these reasons, we might see a different preoperative cognitive trajectory, compared with what we would have seen in a non-COVID-19 time. However, if surgery has an impact on our patient cognition, we still expect to see it as a postoperative change (e.g. a greater decline, a change in slope) compare to their actual preoperative trajectory, so that the performance we see at 3, 6 or 12 months after surgery is worse than what we would expect based on the preoperative trajectory.

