Based on industry web standards, the Cogstate system will communicate with the McMaster system through an Application Programming Interface (API), to generate user- and visit- specific links. The CBB will be host in a McMaster webpage, in a seamless fashion for the participant, who will be directed into the Cogstate application when they start the assessment, and then back to the hosting website upon completion of the tests. The CBB will present each cognitive test to the subject following a self-paced training test until valid cognitive data is provided, enabling testing without supervision. Subjects will receive a simple message at the end of their testing session indicating next steps. A detailed report with cognitive data will not be provided to subjects. For the purpose of this study, a support person will be allowed to attend the self-administration of the CBB. This will be established at the enrolment for each participant, and the participant will be instructed to self-administer the CBB under the same conditions at every assessment over time.

After 1-5 days from the initial recruitment and training session, each participant will self-administer the cognitive testing once, and then every month (i.e. 30 days, ± 1 week) until their surgery is performed. We expect that each participant will have at least 2 assessments before surgery. Participants will then self-administer the CBB 1 month, 3 months, 6 months, and 12 months after surgery.

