3.6.1 Primary analysis

We will report descriptive summary statistics of the performance of the study population at each of the 4 CBB tasks for each of the preoperative and postoperative time points. We will also represent individual and averaged performance trajectories graphically.

To explore whether surgery has a statistically significant impact on cognitive performance and its trajectories, we will model data using interrupted time series analyses. Interrupted time series analysis is a powerful quasi-experimental design to study the longitudinal effects of interventions or exposures, accounting for pre-intervention/pre-exposure trends. We will adopt the approach described in Kontopantelis *et al.*, *BMJ* 2015.^{21 22} According to this approach we will use regression models in which the within patient performance variation over time is partitioned into three main components, to provide independent tests for the slope in scores in the pre-operative period (test 1); the change in level (i.e., absolute change) around surgery, allowing for the trend before surgery (test 2); and the change in slope from before to after surgery (test 3).^{21 22} The preoperative slope quantifies the trend in performance before surgery. The level change is an estimate of the absolute change in cognitive performance that can be attributed to surgery, i.e., between the time points immediately before and immediately after surgery, and accounting for the preoperative trend. The change in slope quantifies the difference between the preoperative and postoperative slope. Based on the hypothesis that the postoperative trajectory will not be homogenous over the 12 months after surgery, we will also adopt a more complex interrupted time series model that will allow for different slopes of change in different time segments, i.e. right before to 1 month after surgery, 1-3 months, 3-6 months, and 6-12 months after surgery.²³ We will conduct the primary analysis first considering only the early-intermediate postoperative performance (up to 6 months after surgery). With the assumption that the

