3.6.2 Secondary Analyses

We will explore whether the effect of surgery on cognitive trajectories differ based on baseline patient characteristics, including age, type of surgery, cognitive performance at baseline, comorbidities, mobility, GDS and pain score. This will be done studying the interaction of these covariates with the components of the interrupted time analysis. The interrupted time series approach as described assumes linearity and constancy of the preoperative trend when projected postoperatively. We will evaluate the validity of these assumptions exploring the association of changes in cognitive performance with intercurrent events other than the index surgery, for the long-term effects.

With a similar approach as for the cognitive performance, we will study the perioperative trajectories of patient physical function/mobility (as indicated by the LLFDI-FC and the life space mobility questions), depressive symptoms (as indicated by the GDS), and of pain (as indicated by the NPRS). We will also explore whether the time-dependent LLFDI-FC, GDS and NPRS scores are associated with the time-dependent cognitive scores.

STATA software, version 15, will be used for the analyses.

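### The 80% power is for a test against a fixed decline of 0.009; the 6-month comparison with an estimated, projected preoperative trend has no power statement, and with 2 to 4 preoperative tests each it stays below 80% unless the within-patient correlation exceeds about 0.92

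*Combined protocol and SAP*

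**What the plan says.** Section 3.5 sets the primary hypothesis on the One-Back Task (OBK) at 6 months after surgery, "compared to what we would expect based on the preoperative trajectory". It says of 330 participants: "This sample size will be sufficient to test our primary hypothesis". The supporting calculation is a one-sample comparison of means ("Based on a test of comparison of means in one sample, with an alpha error of 0.05 (2-tailed"): decline 0.009 under H0, decline 0.035 under H1, SD of the OBK score 0.16, two-sided alpha 0.05, 80% power and 10% attrition. Appendix II gives 0.16 as the SD of the baseline score in healthy older adults.

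The planned analysis is different. Section 3.6.1 fits an interrupted time series with tests for the preoperative slope, the level change and the slope change. It adds a segmented version to "allow for different slopes of change in different time segments". Section 3.6.2 states that the approach "assumes linearity and constancy of the preoperative trend when projected postoperatively".

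On the length of the preoperative series, section 3.4.1 says "We expect that each participant will have at least 2 assessments before surgery", with testing every 30 days (± 1 week) until surgery. Section 1 describes preoperative follow-up "for one to a few months". The primary analysis set in section 3.6.1 ("In our primary analyses, we will include only patients who completed") requires at least two preoperative tests and the 1-, 3- and 6-month postoperative tests.

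**The concern.** The hypothesis compares the observed 6-month score with a value extrapolated from each patient's own preoperative course. Section 1 makes that comparison the reason for the study. The calculation replaces the extrapolated value with the constant 0.009, so the number of preoperative tests, their spacing and the correlation between a patient's scores do not enter it. A slope estimated over one to three months and carried forward six months has a large sampling error.

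There is a second gap. None of the three tests listed in section 3.6.1 is the 6-month contrast that the hypothesis concerns, so the test of the primary hypothesis is not named.

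At stake is how the result is read. If 330 is declared sufficient, a non-significant 6-month contrast could be taken as evidence that surgery has no effect, when the study may be unable to detect the target difference of 0.026.

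**Working it through.** **Inputs from the documents.** Difference to detect 0.035 − 0.009 = 0.026; SD 0.16; two-sided alpha 0.05; power 80%; attrition 10% (section 3.5). At least two preoperative tests, about one month apart (section 3.4.1). Postoperative tests at 1, 3 and 6 months in the primary set (section 3.6.1).

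**Step 1: the plan's own figure.** n = (1.960 + 0.8416)² × 0.16² / 0.026² = 297.2, and 297.2 / 0.9 = 330. The stated size reproduces for a one-sample test against a fixed value.

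**Step 2: what the SD of 0.16 implies.** The SD of a change between two scores is 0.16 × √(2(1 − r)). This equals 0.16 only at r = 0.5. At r = 0.7 it is 0.124 and the one-sample test has 95% power. The SD is therefore conservative for that test if r is above 0.5, and it does not by itself show a shortfall.

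**Step 3: assumptions for the projected comparison.** The documents give neither r nor the distribution of preoperative test counts, so both are varied. Random-intercept model with total SD 0.16; 297 analysed; monthly preoperative tests, the last at surgery; contrast = level change + 6 × slope change; effect 0.026.

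**Step 4: hand check with two tests.** With tests at −1 and 0 months (y1, y2), the projection to month 6 is 7·y2 − 6·y1. The variance of observed minus projected is (1 + 49 + 36)σ² = 86σ², where σ² = 0.16² × (1 − r). At r = 0.5, σ² = 0.0128, the SD is √(86 × 0.0128) = 1.05, the SE with 297 patients is 0.061, and power is 7%.

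**Step 5: full model by generalised least squares.** The SE scales with √(1 − r). For 80% power it must be at most 0.026 / 2.8016 = 0.00928.

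| Preoperative tests | SE, r = 0.5 | SE, r = 0.8 | SE, r = 0.9 | Power at r = 0.5 / 0.8 / 0.9 | r needed for 80% |
|---|---|---|---|---|---|
| 2 | 0.0608 | 0.0385 | 0.0272 | 7% / 10% / 16% | 0.988 |
| 3 | 0.0333 | 0.0211 | 0.0149 | 12% / 23% / 42% | 0.961 |
| 4 | 0.0231 | 0.0146 | 0.0103 | 20% / 43% / 71% | 0.919 |
| 5 | 0.0180 | 0.0114 | 0.0080 | 30% / 63% / 90% | 0.867 |
| 6 | 0.0150 | 0.0095 | 0.0067 | 41% / 78% / 97% | 0.807 |
| 8 | 0.0117 | 0.0074 | 0.0052 | 60% / 94% / above 99% | 0.685 |

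The minimum detectable difference at 80% power is 2.8016 × SE. For 2, 3 and 4 tests it is 0.170, 0.093 and 0.065 at r = 0.5; 0.108, 0.059 and 0.041 at r = 0.8; and 0.076, 0.042 and 0.029 at r = 0.9. The target is 0.026.

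**Step 6: sensitivity.**
- A separate mean at each postoperative visit, in the spirit of the segmented model, changes power for 2 to 4 tests by less than one point.
- With the last preoperative test half a month before surgery, power for 2, 3 and 4 tests is 7%, 11% and 19% at r = 0.5, and 14%, 37% and 66% at r = 0.9.
- With four tests, the r threshold is about 0.89 if every interval is 37 days (last test at surgery), and 0.936 if tests are monthly and the last is a month before surgery.
- Patient slopes that vary but stay constant through surgery leave the SEs unchanged. Between-patient variation in the slope change lowers power: with an illustrative SD of 0.02 per month (not from the documents), four tests at r = 0.8 go from 43% to 36%.

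**The case against.** The strongest reply is that the shortfall rests on inputs the protocol does not give. The range of two to four tests is a reading of the phrase in section 1. Section 3.4.1 sets no maximum, and section 3.5 expects slow reopening and cites a median of 45 weeks to clear the surgical backlog. Patients with long series also supply most of the information on the slope, so mixed counts do better than their shortest members. With half the patients at two tests and half at eight, power is 88% at r = 0.8. With counts spread evenly over two to eight, it is 79% at r = 0.8 and 98% at r = 0.9.

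This is correct, and it means that no single power figure can be assigned to the study. It does not rescue the stated 80%. At r = 0.5, the value implied if 0.16 is also the SD of a change, the mixtures examined give 15% (even over two to four) to 51% (half two, half eight), and eight tests in every patient give 60%. The protocol neither requires nor forecasts long series.

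It can also be said that the objectives are worded as descriptive and exploratory, that the simplification is disclosed, and that the 6-month contrast can be derived from the model. The objectives are so worded, but section 3.5 still states a primary hypothesis with H0, H1, alpha and power. Disclosing the one-sample test does not extend its power to the projected comparison. A contrast that can be derived is still not prespecified.

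**Conclusion.** The concern holds. The 330 and the 80% are arithmetically right for a test against a fixed decline of 0.009, but they do not cover the comparison that section 3.5 attaches them to, because the error in estimating and projecting the preoperative trend is left out. That omission is certain from the text and needs no assumed r.

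The size of the effect is conditional on the model in step 3. With two to four preoperative tests in every patient, power is 7% to 20% at r = 0.5 and 16% to 71% at r = 0.9. Reaching 80% needs r of about 0.92 even with four tests. Adequate power is possible with longer series and high r: five tests at r = 0.9 give 90%, and eight at r = 0.7 give 82%. All figures assume no more than 10% loss; a larger loss from the complete-case primary set would lower them.

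**What to change.** In section 3.5, limit the 80% statement to the comparison with a fixed decline of 0.009, and say what the SD of 0.16 represents and the r it implies for a change score. Add a short table of power or minimum detectable difference for the 6-month OBK contrast from the planned model at N = 330, over a stated range of preoperative test counts (for example 2 to 8, with some mixed-count scenarios) and of r (for example 0.5 to 0.9).

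In section 3.6.1, name that contrast as the test of the primary hypothesis: month-6 level minus the projected preoperative trend, which is level change + 6 × slope change in the three-component model. A sentence saying that a non-significant contrast will be interpreted from its confidence interval would help but is optional.

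The cost is rewording two sections and one table, with no extra patients, visits or data. The drawback is a less favourable stated power for short preoperative series.
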